4.1.4.3 Dose reductions and dose delays

Related SAEs/AEs of \geq grade 2 or non-drug related SAEs/AEs of \geq grade 2 deemed intolerable by the patient or the treating physician and not responding to appropriate medical management will result in a pause until resolution to baseline or grade 1. A pause of a maximum duration of 14 days and a dose reduction to the next lower dose level is allowed if clinically indicated. Only one dose de-escalation step is allowed.

DLT events in any cycle, cases meeting the pre-defined hepatic injury criteria (ref. [5.2.2.1](#)) and infusion related reactions or cytokine release syndromes \geq grade 3 will lead to permanent discontinuation in the dose escalation phases. After recovery to baseline or grade 1 continuation of the cycle at the next lower dose tier is allowed. Only one dose de-escalation step is allowed.

CNS events \geq grade 2 irrespective of relatedness that have not resolved to baseline or grade 1 within one week despite treatment interruption will lead to permanent discontinuation in the dose escalation phase. CNS events that have resolved to baseline or grade 1 within one week can be continued at the next lower dose level. Only one dose de-escalation step is allowed.

In case of dose reductions all future courses will also be at the reduced dose level.

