4.1.4.4 Permanent discontinuation of BI 836909

Patients treated at the initial dose cohort of 0.2 $\mu\text{g}/\text{d}$ who require a dose reduction will be permanently discontinued.

A pause of treatment or delayed start of treatment of more than 2 weeks or several interruptions exceeding a total of 14 days of treatment per cycle due to SAEs/AEs will lead to permanent treatment discontinuation.

Proprietary confidential information.

© 2018 Boehringer Ingelheim International GmbH or one or more of its affiliated companies. All rights reserved.

This document may not - in full or in part - be passed on, reproduced, published or otherwise used without prior written permission.

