4.1.4.5 Temporary treatment interruption of BI 863909

If a pause of treatment < 14 days occurs within a cycle then the cycle will be restarted at the same or the next lower dose (if clinically indicated) and continued until the pre-scheduled end of the cycle. This dose will be continued in subsequent cycles.

If a pause of treatment occurs and less than 7 days of treatment would remain after restart of the cycle there is an option to skip the last treatment days and continue with the next course as scheduled. However, treatment should not be given for less than 14 days per cycle.

Patients who permanently discontinue treatment for reasons other than DLT will be replaced. Only patients who will receive at least 14 days of treatment in the first course will be evaluable for the primary analysis unless they develop DLT.

For dose levels 2 and higher the trial safety committee may decide to start the subsequent cycles of the affected patient and potentially new patients at this and higher dose cohorts in a stepwise fashion: treatment will be started at 10-30% of the target dose for the first week (but not earlier than 4 days after the stop of infusion in retreated patients). On day 9 the dose may be escalated to the target dose.

The re-start of the infusion should be performed in the hospital under supervision of the investigator.

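### Section 4.1.4.3 both orders a permanent stop and permits re-exposure at a lower dose after a drug-related CNS event that is a DLT, and states no precedence

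*Protocol*

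**What the plan says.** Three rules in Protocol Section 4.1.4.3 bear on a CNS event that is also a DLT.

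- **DLT paragraph, first sentence.** "DLT events in any cycle, cases meeting the pre-defined hepatic injury criteria", together with infusion-related reactions or CRS of grade 3 or higher, "will lead to permanent discontinuation in the dose escalation phases".
- **DLT paragraph, second sentence.** "After recovery to baseline or grade 1 continuation of the cycle at the next lower dose tier is allowed". It gives no time limit and names no trial phase.
- **CNS paragraph.** It starts at grade 2. Events "irrespective of relatedness that have not resolved to baseline or grade 1 within one week despite treatment interruption will lead to permanent discontinuation" in escalation; otherwise, "CNS events that have resolved to baseline or grade 1 within one week can be continued at the next lower dose level". It has no upper grade and does not exclude DLTs.

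Section 5.2.1.1 creates the overlap: any drug-related non-haematological event of grade 3 or higher is a DLT. Headache and insomnia are among the grade 3 exceptions, but CNS events as a class are not.

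Section 4.1.4.4 covers permanent discontinuation without mentioning DLTs or CNS events. It stops patients in the 0.2 µg/day cohort "who require a dose reduction will be permanently discontinued", and it stops treatment after "A pause of treatment or delayed start of treatment of more than 2 weeks".

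**The concern.** The first DLT sentence is a mandatory stop. The second DLT sentence and the CNS paragraph are permissions to treat the same patient again. A site facing a recovered grade 3 or 4 CNS DLT cannot tell from the protocol whether re-exposure is allowed or, if it is, whether recovery must have come within one week.

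The first two sentences conflict for every DLT. The CNS case has a further, different rule on top, and the protocol itself treats CNS toxicity as a particular risk: Section 2.3 cites it from another BiTE molecule, and Section 5.2.2.1 makes CNS events of grade 2 or higher events of special interest. With about five sites (Section 3.3), one could stop and another re-expose, and each could point to the same section. At stake is patient safety on re-exposure in a first-in-human trial.

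**Working it through.** The plan states no figure to reproduce. The check traces one case through the rules: a drug-related CNS event that is a DLT, at a dose above 0.2 µg/day, during escalation. It assumes that treatment is paused until recovery to baseline or grade 1.

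**Step 1: is re-exposure permitted?**

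| Recovery | DLT sentence 1 | DLT sentence 2 | CNS paragraph |
|---|---|---|---|
| Within 7 days | No | Yes | Yes |
| Days 8-14 | No | Yes | No |
| After day 14 | No | No (overridden by 4.1.4.4) | No |

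Within one week, one mandatory stop stands against two permissions. On days 8-14, two stops stand against one permission. After day 14 all rules agree. Permission is therefore contested in 2 of 3 windows. Stopping breaches no sentence in any window, because the continuation sentences only permit.

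**Step 2: does another section settle it?** Sections 3.3.4.1, 4.1.4.4, 4.1.4.5 and 5.2.1.1 and the SAP contain no precedence rule. Section 4.1.4.5 says "If a pause of treatment < 14 days occurs within a cycle then the cycle will be restarted", with a one-step reduction where clinically needed, while Section 6.1 moves to the next scheduled cycle after a pause of more than a week. Both govern when dosing resumes, not whether it may resume after a DLT. Where the protocol means to bar re-exposure it can say so plainly: Section 4.1.4.1.4 does this for infusion-related reactions of grade 3 or 4.

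**Step 3: the additional patients.** Both stop sentences are tied to the dose-escalation phase; the continuation sentences are not. Section 3.1 allows up to 6 additional patients at the MTD or recommended dose. If they count as outside escalation, which the text does not make clear, neither stop reaches them and the second DLT sentence lets them continue with no one-week limit.

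**Step 4: where it applies and at what dose.** Table 3.1:1 lists 13 levels. At 0.2 µg/day any needed reduction already means a stop, leaving 13 − 1 = 12 levels. The ratio is the lower dose divided by the causal dose:

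- Between listed levels: minimum 3.2/6.5 = 0.492, maximum 13/25 = 0.520, all others 0.500.
- From the example intermediate levels: 50/75 = 100/150 = 200/300 = 400/600 = 0.667.
- The footnote allows increments of up to 50%, so a smaller increment gives a ratio above 0.667. A step down onto an intermediate level is also higher, for example 75/100 = 0.75.

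**Step 5: effect on the analysis.** Under Section 4.1.4.5 a patient who stops for a DLT is not replaced and remains evaluable. SAP Section 7 keeps patients in their originally assigned cohort, and SAP Section 7.8.1 counts subjects. The patient is one DLT patient at the causal dose under either rule. SAP Section 7.8.1 also tabulates events leading to dose reduction and events leading to discontinuation separately, and SAP Section 7.7 summarises treatment time and cycles. A patient who steps down and one who stops would contribute differently to these.

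**The case against.** The strongest reply is that a workable reading exists. The CNS paragraph could be the specific rule that overrides the general DLT rule, or the stops could apply in escalation and the permissions only afterwards. Neither is stated. The DLT rule is the more specific one on severity and relatedness, and the second DLT sentence directly follows the stop as if it concerned the same patient.

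Oversight is also substantial. Events of special interest are reported within 24 hours (Section 5.2.3), the sponsor evaluates adverse events continuously (4.1.4.2) and controls dose allocation (4.1.4), drug release goes through IWRS (6.2.4), re-starts take place in hospital (4.1.4.5), and the investigator may stop at any time (3.3.4.1). These safeguards make divergent handling less likely and less dangerous, and that part of the reply stands. They do not decide whether re-exposure is permitted.

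It is also fair to say that the conflict between the two DLT sentences is wider than CNS events. That is a reason to review the whole paragraph, not to leave the CNS case open.

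A reader might infer that the protocol compels re-exposure, or that the contradiction undermines the MTD. The documents support neither: the continuation sentences are permissive, and the DLT count is the same under both rules. The opposite inference, that nothing in the SAP output is affected, also goes too far (step 5).

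**Conclusion.** The point holds as an internal contradiction in a safety rule and should be corrected. For a CNS event that is a DLT, Section 4.1.4.3 does not settle whether treatment may resume or whether the one-week limit applies. The contradiction covers recoveries up to day 14 at 12 of 13 listed levels. Those counts show where the text is ambiguous; they do not measure risk. The documents give no frequency for CNS DLTs, so the number of patients affected cannot be estimated.

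If re-exposure is taken as permitted, the dose is about half the causal dose on the listed scale, two-thirds from the example intermediate levels, and a larger fraction where intermediate steps are smaller. The DLT count, MTD rule and SAP methods do not change. The contents of the dose-reduction, discontinuation and exposure summaries do depend on the rule. The conclusion rests on reading the sentences as written, with no unstated precedence or phase restriction.

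**What to change.** Add one sentence to the CNS paragraph of Section 4.1.4.3:

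> A CNS event that meets the DLT definition in 5.2.1.1 leads to permanent discontinuation, in the dose-escalation phase and in the additional patients treated at the MTD or recommended dose; this takes precedence over both continuation sentences in this section, and the one-week step-down applies only to CNS events that are not DLTs.

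Naming the additional patients matters. A sentence limited to escalation could leave them under the looser second DLT sentence.

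If the sponsor and safety committee prefer to allow step-down after CNS DLTs, the sentence must override both DLT sentences and keep the one-week limit. Overriding only the second would leave the mandatory stop in conflict.

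This settles CNS DLTs only. Any wider rewording of the DLT paragraph has to be aligned with Section 4.1.4.1.4, where the CRS table permits re-start after grade 3 and the infusion-reaction rule does not.

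The cost is one sentence in an amendment, which needs ethics and authority approval (Section 8.1) and can go with the next one. It adds no visits or procedures and changes no SAP method. The downside of the stricter rule is that a patient who recovers quickly from a CNS DLT loses the option of continuing at a lower dose.

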4.1.4.4 Permanent discontinuation of BI 836909

Patients treated at the initial dose cohort of 0.2 $\mu\text{g}/\text{d}$ who require a dose reduction will be permanently discontinued.

A pause of treatment or delayed start of treatment of more than 2 weeks or several interruptions exceeding a total of 14 days of treatment per cycle due to SAEs/AEs will lead to permanent treatment discontinuation.

Proprietary confidential information.

© 2018 Boehringer Ingelheim International GmbH or one or more of its affiliated companies. All rights reserved.

This document may not - in full or in part - be passed on, reproduced, published or otherwise used without prior written permission.

4.1.4.5 Temporary treatment interruption of BI 863909

If a pause of treatment < 14 days occurs within a cycle then the cycle will be restarted at the same or the next lower dose (if clinically indicated) and continued until the pre-scheduled end of the cycle. This dose will be continued in subsequent cycles.

If a pause of treatment occurs and less than 7 days of treatment would remain after restart of the cycle there is an option to skip the last treatment days and continue with the next course as scheduled. However, treatment should not be given for less than 14 days per cycle.

Patients who permanently discontinue treatment for reasons other than DLT will be replaced. Only patients who will receive at least 14 days of treatment in the first course will be evaluable for the primary analysis unless they develop DLT.

For dose levels 2 and higher the trial safety committee may decide to start the subsequent cycles of the affected patient and potentially new patients at this and higher dose cohorts in a stepwise fashion: treatment will be started at 10-30% of the target dose for the first week (but not earlier than 4 days after the stop of infusion in retreated patients). On day 9 the dose may be escalated to the target dose.

The re-start of the infusion should be performed in the hospital under supervision of the investigator.

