All trial relevant documentation will be stored in BIRDS. Trial relevant documentation which has to be at the trial site will be filed in the ISF at the investigator site. The ISF document will be kept in print-out version at the sites as far as required by local regulation and BI-SOP.

A safety committee (SC) of the investigators in cooperation with the responsible trial monitor and the medical project leader of the sponsor as well as medical representatives from Amgen will be implemented to analyse ongoing safety information and decide on further steps in dose finding. Prior to escalating the dose to the next higher dose cohort there will be a safety teleconference or meeting between trial investigators and the medical project leader of the sponsor to discuss any findings in the ongoing and already recruited cohorts, this means that all available clinical and safety data including repeated cycles of prior dose cohorts will be taken into consideration for assessments and decision making. Participation of the coordinating investigator or [REDACTED] deputy is a mandatory requirement for this committee to establish a quorum. After the defined observation period of each cohort this safety committee will discuss the need to enter additional patients or dose cohorts or release the next dose cohort and dose increment as per protocol. The same is true for the decision to switch from single patient cohorts to the 3+3 design. Step dosing may be implemented based on cytokine release syndrome qualifying for DLT following the following guidance:

- Restart with previous dose level for 4 days (one bag) and then escalate to current dose level until the end of the cycle.

The composition of the SC will be documented in BIRDS. The tasks and responsibilities will be agreed in contracts between the SC members and the Sponsor. SC will decide on the switch from single patient cohorts to the 3+3 design independently from defined dose cohorts based on clinical activity (antitumor response) and/or clinically relevant safety or pharmacodynamics findings.

Data Management and Statistical Evaluation will be done by BI according to BI SOPs.

Tasks and functions assigned in order to organise, manage, and evaluate the trial will be defined according to BI SOPs. A list of responsible persons and relevant local information can be found in the ISF.

Summary of assessments (see corresponding [Flow charts](#)):

Proprietary confidential information.

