5.2.1.1 Dose limiting toxicity

Dose limiting toxicity (DLT) is defined as any drug-related non-haematological adverse event CTCAE version 4.03 grade 3 or higher. The following grade 3 events will not be considered

Proprietary confidential information.

© 2018 Boehringer Ingelheim International GmbH or one or more of its affiliated companies. All rights reserved.

This document may not - in full or in part - be passed on, reproduced, published or otherwise used without prior written permission.

DLT: febrile neutropenia and infection responding to antibiotic/anti-infective treatment within 48 hours, fatigue, headache, insomnia, fever, hypotension.

Laboratory parameters of grade ≥ 3 but not considered clinically relevant and/or responding to routine medical management, will not be considered dose limiting toxicities.

Additional events that are considered DLT include:

- Persistent grade 4 neutropenia or thrombocytopenia until day 56 in the absence of detectable Multiple Myeloma as it may reflect a marrow toxic effect of BI 836909.

If infusion related reactions (IRR) or cytokine release syndromes (CRS) \geq grade 2 occur or constitute DLT events the safety committee may decide to switch to step dosing for the respective and any higher dose cohort. In that case the infusion will be started at 10(-30)% of the target dose on day 1 of the course and will be escalated to the full target dose from day 9 of course 1 on for the remainder of the course. Patients will be hospitalized and pre-medicated for the dose increase the same way they are for start of treatment. Once the safety committee decides to switch to step dosing patients that may have developed DLT due to IRR or CRS events may be replaced at the respective cohort by additional patients who will receive treatment with the adapted administration schedule (step dosing).

Although hematological adverse events (e.g. anemia, thrombocytopenia, neutropenia, lymphopenia) will not be considered DLT, complications resulting from hematological events, e.g. bleeding due to thrombocytopenia or grade 4 infection due to neutropenia are classified as non-hematological adverse events and are covered by the above definition of DLT. Nevertheless, hematological adverse events will be considered for definition of the dose for further development.

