6.3 SUBJECT SETS ANALYSED

All entered subjects who received trial medication will be included in the safety analysis and in the pharmacokinetic analysis set depending on the availability of measurement values and on their adherence to the CTP. The criteria for inclusion into these populations are defined as follows:

Populations: Please see below for the specified populations.

Treated set (TS): all patients who were administered study medication. This set of patients is used for all analyses except for analysis of PK data.

[figure not shown]
MTD evaluation set (MTDS): all patients in the TS who were not replaced for the MTD determination. Rules for replacement of patients were defined in CTP, Section 4.1.4.5. In addition safety committee will decide the replacement of patients.

PK Analysis Set (PKS): all evaluable patients in the treated set which provide at least one evaluable observation for at least one PK endpoint.

The TS will be used for all efficacy and safety analyses. In addition, the MTDS represent the populated used for MTD determination. The primary analyses of DLTs during 1st cycle will be based upon the MTDS. PK analyses will be based on the PKS. Refer to Protocol Section 7.3.5 on handling PK endpoints.

Table 6.3: 1 Subject sets analysed

Class of endpoint	Treated set	Subject set	
		MTDS	PKS
Primary and key secondary endpoints	X	primary analysis	
Other secondary and further endpoints	X		
Safety endpoints	X		
Demographic/baseline endpoints	X		
PK endpoints			X

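### The 14-day evaluability rule names no dose, so a patient reduced early in cycle 1 for a non-DLT event counts as a non-DLT patient at the assigned dose, which can push the MTD upward

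*Protocol*

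**What the plan says.** Protocol 4.1.4.5 defines who counts for the MTD: "Only patients who will receive at least 14 days of treatment in the first course will be evaluable for the primary analysis unless they develop" a DLT. The dose given on those days is not mentioned.

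Other rules allow cycle 1 days below the cohort dose:

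- **In-cycle reduction.** After a pause of under 14 days, 4.1.4.5 says "then the cycle will be restarted at the same or the next lower dose (if clinically indicated"). Section 4.1.4.3 allows a one-level reduction after adverse events of grade 2 or higher, and adds that "CNS events that have resolved to baseline or grade 1 within one week can be continued at the next lower dose level". All later courses then stay at the reduced dose.
- **Step dosing.** Under 5.2.1.1, "the infusion will be started at 10(-30)% of the target dose on day 1 of the course" and it "will be escalated to the full target dose from day 9 of course 1 on for the remainder of the course". Section 3.1.1 describes a different schedule: "Restart with previous dose level for 4 days (one bag) and then escalate to current dose level until the end of the cycle".

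The replacement rule in 4.1.4.5 covers patients who stop treatment permanently for reasons other than DLT. SAP 6.3 defines the MTD evaluation set (MTDS), used for the primary DLT analysis, as "all patients in the TS who were not replaced for the MTD determination". It refers back to 4.1.4.5 and adds that the safety committee decides on replacements, without giving a criterion. SAP 7 analyses every patient in the assigned dose cohort. SAP 7.3 defines non-compliance by the same 14-day count, again without a dose.

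**The concern.** A 3+3 decision treats each evaluable patient without a DLT as evidence that the cohort dose is tolerated. That holds only if the patient received the cohort dose for long enough. Under the rules above, a patient can leave the cohort dose after a few days because of a grade 2 event, complete cycle 1 one level lower, and still enter the count as 0 DLT at the higher dose.

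This does not need an unusual combination of rules. DLTs are in general related non-haematological events of grade 3 or higher, and 5.2.1.1 also exempts several grade 3 events. The CRS table in 4.1.4.1.4 itself raises a reduction from 400 to 200 µg/d after two consecutive grade 2 events, so non-DLT reductions are foreseen. At stake is the primary endpoint. Each level is decided on 3 to 6 patients and the next planned step is about two-fold, so one miscounted patient matters.

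**Working it through.** The plan states no DLT rate, power or operating characteristic, so it has no figure of its own to reproduce. The check has two parts.

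**1. Days at the cohort dose (from the documents)**

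- *Reduction.* Take a patient in the 400 µg/d cohort with a related grade 2 CNS event on day 3, a pause, and a restart at 200 µg/d on day 10. Days at 400: 2 (days 1–2). Days at 200: 28 − 9 = 19. Total 2 + 19 = 21, which is at least 14. The patient is evaluable with 0 DLT at 400. Treatment was not permanently stopped, so the stated replacement rule does not apply.
- *Step dosing, 5.2.1.1 schedule.* A completed cycle gives 28 − 8 = 20 days at target. At the 14-day minimum it is 14 − 8 = 6, but that also needs days lost to a pause or skipped at the end.
- *Step dosing, 3.1.1 schedule.* Completed cycle 28 − 4 = 24 days; at the minimum 14 − 4 = 10.

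**2. Effect on the decision (illustrative)**

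Protocol 3.2 says the MTD is exceeded if at least 2 of up to 6 patients have a DLT. The following assumptions are not in the documents. Let p be the DLT risk over 28 days at the cohort dose, with constant hazard and no DLT risk on days below that dose. A patient with d days at the dose then has risk u = 1 − (1 − p)^(d/28). Reduction is taken as unrelated to the patient's own DLT risk.

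With one such patient among six:

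P(at most 1 DLT) = (1 − p)^5 + 5p(1 − p)^4(1 − u)

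For p = 0.33 and d = 2, u = 1 − 0.67^(2/28) = 0.028, and P = 0.135 + 0.3325 × 0.972 = 0.458. With full exposure u = p, and P = 0.135 + 0.3325 × 0.67 = 0.358.

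With two such patients:

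P = (1 − p)^4(1 − u)^2 + 4p(1 − p)^3(1 − u)^2 + 2u(1 − u)(1 − p)^4

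| p | All six at 28 days | One at 2 days | Two at 2 days | One at 6 days | Two at 6 days |
|---|---|---|---|---|---|
| 0.25 | 0.53 | 0.62 | 0.72 | 0.61 | 0.69 |
| 0.33 | 0.36 | 0.46 | 0.58 | 0.44 | 0.53 |
| 0.40 | 0.23 | 0.33 | 0.45 | 0.31 | 0.41 |

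*Early DLTs.* If a share f of the cumulative hazard has passed before the reduction, u = 1 − 0.67^f at p = 0.33. For f = 0.5, u = 0.181, and one such patient gives 0.135 + 0.3325 × 0.819 = 0.41. For f = 0.9, u = 0.303, which gives 0.135 + 0.3325 × 0.697 = 0.37, against 0.36 with full exposure.

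*What a 14-day minimum at target buys.* At d = 14, u = 0.181. One patient at exactly that minimum gives 0.41 and two give 0.46. If all six had only the minimum, P = (1 − u)^6 + 6u(1 − u)^5 = 0.70, against 0.92 for 6 days and 0.36 for 28.

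**The case against.** **Step dosing.** Once the safety committee switches a cohort to step dosing, the stepped schedule is that cohort's regimen, and a completed cycle has 20 target-dose days. This stands. A reader might infer that stepped patients typically count after only 6 days at target. The documents do not support that: under 4.1.4.5 an interrupted cycle normally resumes and runs to its scheduled end.

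**Escalation is not mechanical.** The safety committee reviews all available clinical and safety data before each step (3.1.1), can add patients or intermediate cohorts (3.1), and can replace patients (SAP 6.3). A grade 2 CNS event is an adverse event of special interest, reportable within 24 hours (5.2.2.1, 5.2.3). Adverse events leading to dose reduction get their own table (SAP 7.8.1), and up to 6 further patients are treated at the MTD or recommended dose. These points soften the effect, but none sets a minimum exposure at the cohort dose. The review of later-cycle events in 5.2.1 cannot supply the missing exposure either, because reduced patients stay reduced.

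**A grade 2 event is not a DLT by design, and a DLT after a reduction still counts against the assigned cohort.** Both are true. The point is not that grade 2 events should be DLTs, but that the patient was not observed at the dose being judged. The second fact offsets only part of the effect.

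**DLTs may come early.** The 48-hour stagger and the hospital stay at the start of cycle 1 suggest that the protocol expects early cytokine release. If so, the effect is small, as the f = 0.9 case shows.

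**Fourteen days at target is still only half of 28.** This stands too. The 14 days are the protocol's own threshold, and tying them to the dose removes only part of the gap.

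**Conclusion.** The point holds for in-cycle reductions. Read together, protocol 4.1.4.3 and 4.1.4.5 and SAP 6.3 and 7 count a patient as a non-DLT patient at a dose received for only a few days. The direction is upward, provided DLT risk does not fall with dose and time at dose.

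The size is unknown. In the illustration at p = 0.33, one patient of six with 2 days at dose moves the chance of at most one DLT from 0.36 to 0.46 under constant hazard, and to 0.37 if 90% of the hazard has already passed. If patients who need an early reduction are also more prone to DLTs, the effect would be larger than this model shows.

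A reader might infer that the MTD from this trial is too high by a known margin, or that most decisions would be affected. The documents support neither. They give no DLT rate, no DLT timing and no number of reduced patients, and safety committee judgement stands between the count and the next dose. Step dosing alone is a minor route. This is a gap in the primary-analysis definition that is worth closing, not a fatal flaw.

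**What to change.** 1. **Protocol 4.1.4.5 and the MTDS in SAP 6.3.** For cohorts of 3.2 µg/d and above, define MTD-evaluable as at least 14 days of cycle 1 infusion at the cohort's assigned target dose, or a DLT. Step-dose run-in days and reduced-dose days do not count. The limit to these cohorts is needed because the single-patient levels have a 2-week DLT window, and 14 target-dose days after an 8-day run-in end on day 8 + 14 = 22.
2. **Replacement.** State that patients without a DLT who fall short are not counted as non-DLT patients in the 3+3 and are replaced even if they continue at a reduced dose. The current rule covers only permanent discontinuation.
3. **Visibility.** Replacing these patients silently would hide early intolerance. Report them to the safety committee, and show them in the DLT table by cohort with the reason for reduction. Keep the all-treated DLT count as a sensitivity analysis; SAP Table 6.3: 1 already lists the treated set for the primary endpoints.
4. **Step dosing.** The schedules in 3.1.1 and in 4.1.4.5/5.2.1.1 give different numbers of days at the cohort dose and must be reconciled.

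The cost is a few sentences in each document and an occasional extra replacement patient. A patient who completes a stepped cycle under 5.2.1.1 still qualifies, with 20 − 14 = 6 days to spare.
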